4 ANTICIPATED COMPLICATIONS AND ADVERSE EVENTS

4.1 Anticipated Complications

For this study, a complication is defined as the following: morbid event or consequences of a morbid event. While all complications will be summarized in the final report, the primary focus of the analysis will be complications involving the vascular system, such as transient ischemic attack (TIA), amaurosis fugax, stroke, symptomatic carotid occlusion, thrombosis, bleeding, and death. The terms “adverse event” and “complication” will be used interchangeably.

An Adverse Event (AE), Unanticipated Adverse Effect (UAE) and Serious Adverse Event (SAE) are defined in Appendix E. All AEs, UAEs and SAEs that occur during the course of the study (until the completion of the final follow-up visit), whether observed by the investigator or by the patient, and whether or not thought to be PhotoFix related, will be reported in detail on the Adverse Event eCRF and followed to a satisfactory resolution. The investigator will follow the patient until the event resolves. In the unusual circumstance that the event has not resolved by the time of the patient’s completion of the study, an explanation will be entered on the Adverse Event eCRF; the circumstance may be determined to be a permanent condition, and will be documented as such.

Secondary morbid events will not be included in the calculation of device-related complication rates. A morbid event should be documented only once unless there are multiple occurrences of that event.

Consequences of morbid events, such as explant, mortality, and reoperation will be captured on the Adverse Event eCRF, which details the associated event. In the case of an explant, additional information will be captured on the Explant eCRF (Appendix D).

Potential complications that may occur with any vascular surgery include, but are not limited to:

- Allergic reaction to medication
- Bleeding
- Breathing difficulty
- Chest pain
- Heart attack
- Infection (ex. pneumonia, urinary tract infection, wound infection)
- Irregular heartbeat
- Lung or kidney failure
- Memory loss
- Pain
- Sickness/ nausea
- Stroke
- Thrombosis

Complications specific to the use of the PhotoFix may include, but are not limited to the following:

- Abscess
- Adhesion

- Blood leakage through suture line, holes, or tears
- Calcification/mineralization
- Complete heart block (arrhythmia)
- Death
- Inflammatory immune response
- Infection
- Intimal hyperplasia
- Rejection

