6.1 Study Endpoints & Variables

In the case of CEAs, the primary endpoint of the study will be rate of ipsilateral central neurologic events.

- Ipsilateral central neurologic events: Transient ischemic attack, amaurosis fugax, stroke, and symptomatic carotid occlusion.

In the case of all other (non-CEA) vascular procedures, the primary endpoint of the study will be primary patency in the target artery or vein.

- Primary patency (of target vessel): Loss of patency will be determined by the loss of previously palpable pulses, patients presenting with recurrent symptoms, a drop in ABI >0.15 in the case of lower limb artery repair, Doppler ultrasound findings of occlusion, angiography of the affected vessel or a combination of these.

The secondary endpoints of the study will include: overall survival rate, all-cause reoperation rate, device-related reoperation rate, explant rate, restenosis rate, adverse event rate, and secondary patency (HAR only).

- Overall Survival:
 - Early mortality: Death < 30 days following PhotoFix implantation.
 - Late mortality: Death ≥ 30 days following PhotoFix implantation, until last day of follow-up.
- All-Cause Reoperation Rate: The total number of reoperations required in patients over the follow-up period, which include the repair or alteration of the surgical area around the patch.

- **Device-Related Reoperation Rate:** The total number of unplanned reoperations required in patients over the follow-up period, which are determined by the surgeon to be device-related.
- **Explant Rate:** The total number of device explants over the course of follow-up. Explants will include the removal of PhotoFix for any reason after implantation.
- **Restenosis Rate:** The total number of documented cases of stenosis documented as the recurrence of abnormal narrowing of a vessel after corrective surgery.
- **Adverse Event Rate:** The total number of any unfavorable and unintended sign (including an abnormal laboratory finding), symptom, or disease temporarily associated with the use of a device, whether or not related to the device.
- **Secondary Patency (HAR only):** The time from implantation to the point where the access is abandoned.

Statistical analysis will be used to assess all study endpoints as applicable.

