6.7 Statistical Analysis Plan

Enrolled patients will be described in aggregate and by indication (as deemed appropriate); baseline characteristics will include, but not limited to, age, sex, race, ethnicity, body mass index (BMI), comorbidities, fundamental diagnosis/etiology, and pertinent surgical history. Operative details will be described in aggregate and include a summary of the types of procedures performed, by relevant category. Parameters with continuous data types will be summarized using descriptive statistics, i.e., mean, standard deviation, and range. Categorical clinical parameters will be summarized based on percentages.

Ipsilateral central neurologic event rate, overall survival, re-operation rate, explant rate, and restenosis rate ($\geq 50\%$ stenosis) will be summarized based on percentages of affected patients and included in a table, which will summarize the endpoints in aggregate and by surgical indication (ex. CAS, ESRD, PAD, AAA, etc.). The summary of ipsilateral central neurologic event rates will include all events (transient ischemic attack, amaurosis fugax, stroke, and symptomatic carotid occlusion), as well as the incidence of each event individually.

Additional analysis of follow-up data will also be performed with the Kaplan-Meier method, as deemed appropriate by the incidence of events. Kaplan-Meier plots may be generated for endpoints including overall survival, primary patency, secondary patency, as well as freedom from ipsilateral central neurologic event rate, re-operation, explant, and restenosis ($\geq 50\%$ stenosis). Kaplan-Meier plots for survival will include the following mortality classifications: all causes of mortality, vascular-related mortality and device-related mortality (as applicable). The remaining plots will be specific to indication, if the sample sizes allow for the creation of meaningful plots.

The incidence of adverse events will be categorized and summarized with percentages for the aggregate sample. Adverse events will be divided into early and late post-operative events to represent the distribution of occurrences. Events will be considered as early events if the event occurs <30 days after the operation, while late post-operative events will be considered to be all events happening after this time period. Early and late events will be presented by indication for surgery, seriousness of event, and relation to PhotoFix. Adverse events occurring secondary to

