5. Classify the event as one of the following (if multiple symptoms, classify by most severe)	 Amaurosis Fugax  Bleeding event  Cardiac event  Endoleak  Infection  Inflammation/Edema  Pain  Paraparesis  Renal event  Stroke  Symptomatic Carotid Occlusion  Thrombosis  Trauma  Transient Ischemic Attack  Other: _____
(Infection only), was a culture taken?	 Yes  No
(Infection only), If yes, what were the reported results?	 Inconclusive  Positive (identify organisms): _____  Negative  Report not available
6. Describe the Event	
7. Consequence of Adverse Event	 Surgical Intervention  Hospitalization (New or Prolonged)  Death  Other: _____  None

*Select all that apply

Adverse Event eCRF	
If death is indicated, provide cause of death	 Unknown
8. Required Drug Treatment *Update Medication eCRF, as applicable	 Yes  No  Unknown
9. Classify the Adverse Event. *Refer to Protocol Appendix E, Definitions	 Adverse Event (AE)  Unanticipated Adverse Effects (UAE)  Serious Adverse Event (SAE)
If SAE, select at least one of the following	 Death  Life Threatening  Other Medically Important Serious Event  Persistent/ Significant Disability  Requires or Prolongs Hospitalization *Select all that apply
10. Is the event related to the subject's vascular surgery?	 Yes  No
11. Is the Adverse Event related to PhotoFix?	 Definitely  Probably  Possibly  Unrelated

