#### **Incidence of Central Neurologic Events:**

- Percent of patients who experienced at least one transient ischemic attack
- Percent of patients who experienced at least one case of amaurosis fugax
- Percent of patients who experienced at least one stroke
- Percent of patients who experienced symptomatic carotid occlusion at least once
- Percent of patients who experienced any of the central neurologic events of interest at least once

- (All Non-Carotid Indications)

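### The Adverse Event form codes one category per event, so a CEA component rate is undercounted when two components occur in the same event

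*Protocol*

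**What the plan says.** Protocol 6.1 defines the CEA primary endpoint by four components: "Ipsilateral central neurologic events: Transient ischemic attack, amaurosis fugax, stroke, and symptomatic carotid occlusion". Protocol 6.7 will summarise all of them together, "as well as the incidence of each event individually". SAP 2.9.1 turns this into patient-level percentages, one per component, for example "Percent of patients who experienced at least one transient ischemic attack" and "Percent of patients who experienced symptomatic carotid occlusion at least once", and then the composite: "Percent of patients who experienced any of the central neurologic events of interest at least once".

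The events are captured on the Adverse Event eCRF in Protocol Appendix D. Item 5 reads "Classify the event as one of the following (if multiple symptoms, classify by most severe", followed by 15 options. Four are the endpoint components. The other eleven include thrombosis, cardiac event, bleeding event and a catch-all. Item 5 is not multi-select, although item 7 and the SAE sub-question of item 9 on the same form are. Item 6 is free text: "6. Describe the Event".

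On the unit of reporting, Protocol 4.1 says "A morbid event should be documented only once unless there are multiple occurrences of that event".

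SAP 2.10 promises counts and percentages for CEA patients but names no source field and no derivation. SAP 2.17 provides for manual classification only of events filed in the catch-all category.

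**The concern.** The analysis needs four yes/no indicators per patient, and these can be true together. The coded field supplies one value per event. The components are not mutually exclusive: an occlusion counts only if it is symptomatic, and the other three components are neurologic presentations that could accompany it. A site that follows item 5 as written records one and leaves the other out of the coded data.

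The form asks for the most severe category, but the documents give no order of severity across the 15 options. The carotid stenosis grade in Appendix E orders amaurosis fugax, TIA or minor stroke, and major stroke, but it gives occlusion no place. Sites may therefore choose differently for the same clinical picture.

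The study is single-arm and descriptive, so the observed percentages are themselves the result. An undercount in a primary-endpoint component goes straight into the report.

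**Working it through.** The plan states no figure on this point: there is no CEA target and no expected event rate. The check therefore maps the form onto the SAP 2.9.1 quantities and then sizes the effect under stated assumptions.

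**Three cases follow from item 5.**

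1. *Components occur as separate events.* Each has its own record. All component rates and the composite are correct.
2. *Two components occur in one event.* One is coded. The other component's count falls by one patient, unless that patient has it on another record. The composite is unchanged, because the coded component still qualifies the patient.
3. *A component occurs within an event coded to a non-component category* (e.g. thrombosis or cardiac event). That component's count falls by one, and so does the composite, if the patient has no other qualifying record.

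**Size of one lost patient.** The change in a rate is 1/N, where N is the number of CEA patients (assumed):

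- N = 30: 1/30 = 3.3 points
- N = 50: 1/50 = 2.0 points

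**Illustration.** Assume three affected CEA patients: A has a stroke only; B has a stroke and a symptomatic occlusion on one form, coded as stroke (case 2); C has a stroke within an event coded to a non-component category (case 3).

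| Quantity | True count | Coded count | N = 30, true vs coded | N = 50, true vs coded |
|---|---|---|---|---|
| Stroke | 3 (A, B, C) | 2 (A, B) | 10.0% vs 6.7% | 6.0% vs 4.0% |
| Symptomatic carotid occlusion | 1 (B) | 0 | 3.3% vs 0% | 2.0% vs 0% |
| Composite | 3 (A, B, C) | 2 (A, B) | 10.0% vs 6.7% | 6.0% vs 4.0% |

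Exact (Clopper-Pearson) 95% limits for the composite at N = 50 are 1.3 to 16.5% for 3/50 and 0.5 to 13.7% for 2/50.

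Without patient C, the composite is 2 true and 2 coded, so there is no loss. Occlusion is still 1 true and 0 coded. The component bias therefore arises from overlap alone, while the composite bias needs case 3.

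**Is recovery planned?** Item 6 text, supporting notes for each event (Protocol 4.3) and intended full source verification (Protocol section 7) hold the missing information. Follow-Up eCRF items 5 to 8 may also show lost patency, reoperation, restenosis or other events. But SAP 2.17 reclassifies only catch-all events, and SAP 2.10 sets no review. A form completed exactly as item 5 instructs is not inconsistent with its source, so it need not raise a query under Protocol 6.5. By contrast, SAP 2.9.1 does specify a cross-form check and query for primary patency.

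**The case against.** The strongest reply is that the information is not lost. The form is completed per event, so separate events are each coded. The text, source notes, verification and follow-up items give a data manager several routes to a second component. The SAP does not say that the endpoint is computed from item 5 alone. The study has no hypothesis test or threshold, and the intervals with and without one event overlap almost entirely.

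Most of this stands, and it rules out several stronger readings that a reader might infer:

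- *The component rates cannot be derived at all.* Not supported. They are derivable for separate events and recoverable, though not by plan, for combined ones.
- *Protocol 4.1 bars a second form.* Not supported. It bars recording the same event twice. Protocol 6.7 says that events secondary to another complication are collected, so a distinct TIA after a thrombosis can have its own record.
- *Overlap among the components lowers the composite.* It does not; only case 3 can.
- *Carotid occlusion could be missed entirely, or is the component most closely tied to the patch.* Nothing in the documents supports either. Occlusion has its own option, and a site may equally rank it above a TIA or amaurosis fugax.

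What the reply does not answer is that item 5 is an explicit instruction which, when followed, gives a wrong coded value in case 2, and the SAP contains no step that would correct it.

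**Conclusion.** The concern holds in a limited form. When two CEA components occur in one event, the coded field drops one, and that component's reported rate is biased low. The composite is exposed only where a component is filed inside an event coded to a non-component category and the patient has no other qualifying record. In both situations the coded rate can only be too low.

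Each patient lost lowers a rate by 2.0 to 3.3 points if there are 50 to 30 CEA patients. That range is an assumption, and the documents give no basis for estimating how often such events would occur. The illustration shows the mechanism; it does not predict the size of the bias.

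This is a moderate point. It does not invalidate the CEA endpoint, but it affects how a primary endpoint is captured and is cheap to correct.

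**What to change.** Change the form in one of two ways:

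- make item 5 of the Adverse Event eCRF multi-select, with a separate primary-category field so that the adverse event table in SAP 2.17 still counts each event once; or
- keep item 5 and add four yes/no items for CEA patients, one per component.

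Then state in SAP 2.9.1 and 2.10 that a CEA patient counts for a component if any post-implant adverse event record marks it, and for the composite if any of the four is marked.

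If the form is already locked, pre-specify a review of item 6 and the source notes for every adverse event in CEA patients, including those coded to a non-neurologic category, with the component indicators recorded before data lock.

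The cost is a small eCRF edit and one SAP sentence or, for the fallback, reading time. Component rates, and occasionally the composite, may come out slightly less favourable.

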3 EXPERIMENTAL DESIGN

3.1 Type of Study

This study is a prospective, multicenter, post-market clinical follow-up study to evaluate PhotoFix safety outcomes in vascular repair and reconstruction surgery. This is an observational study on a currently marketed device; no study activities are experimental.

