8 PATIENT WITHDRAWAL

At the discretion of the physician, a patient can be removed from the study at any time without the patient's consent for the following reasons: a) it is in the best interest of the patient to be withdrawn from the study; b) patient non-adherence to the study protocol requirements; c) patient, sponsor or investigator request; d) the investigator may also elect to withdraw the patient from the study at any time based on their medical judgment.

A patient will be considered Lost to Follow-up and therefore terminated from the study when the following criteria are met: failure to complete two consecutive follow-up visits (without due cause) AND documentation of three unsuccessful attempts by the investigator or his/her designees to contact a patient or next of kin, including at least one registered letter.

Subjects who request discontinuation from the study prior to completion will be encouraged to complete their study follow-up visits, particularly the 6-month visit; at a minimum, the patients can be followed per protocol for safety.

It is the responsibility of the treating physician to notify the Sponsor of any patients removed from the study.

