12. Status of Adverse Event	 Resolved  Resolved with Sequelae  Not Resolved  Fatal  Unknown
13. Does the Adverse Event Require Study Discontinuation? If yes, complete the End of Study eCRF	 Yes  No

Explant eCRF	
Study Subject ID	
1. Date of Explant	____ / ____ / ____ Month/Day/Year
2. Primary Reason for Explant *Complete Adverse Event eCRF	 Infection  Patch Aneurysm  Patch Deterioration  Rupture  Suture Line Tear  Other: _____
3. Macroscopic evidence of the following:	 Calcification  Fibrous Sheathing  Host Tissue Overgrowth  Infection  Inflammation  Thrombosis  Tissue Rejection  Other  Unknown *select all that apply
If any macroscopic findings, provide additional detail.	
4. Was there a pathological analysis of the explanted specimen?	 Yes  No  Unknown
If yes, what were the documented pathology results?	
5. Planting Surgeon	
6. Description of Surgical Procedure	
7. Was the entire PhotoFix patch removed?	 Yes  No  Unknown
8. Was peri-operative imaging completed? *If yes, complete the Imaging Evaluation eCRF	 Yes  No  Unknown
9. Were photographs taken of the explanted tissue? *If yes, please e-mail photographs to CryoLife	 Yes  No  Unknown

End of Study eCRF	
Study Subject ID	
1. Date of Discontinuation	/ / Month/Day/Year
2. Indicate Associated Visit	 Visit 1, Pre-op  Visit 2, Peri-Op/Immediately post-op  Visit 3, 1 month post-op  Visit 4, 3 months post-op  Visit 5, 6 months post-op  Unscheduled Visit

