3. Did the patient complete the study?	 Yes  No
If no, Reason for Discontinuation *Complete Adverse Event eCRF, as applicable	 Adverse Event  Death  Did not meet inclusion/ exclusion criteria  Investigator Judgement  Lost-to-Follow-Up  Non-compliance  Pregnancy  Protocol Violation  Termination of Study by Sponsor  Withdrew Consent  Other: _____
If no, provide Details on Discontinuation	 No additional details

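### Outcome collection may stop after an adverse event or a physician's removal of the patient, so later endpoint events may be lost and 6-month estimates may be too favourable

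*Protocol*

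**What the plan says.** - **Adverse Event eCRF, item 13 (Protocol Appendix D).** It asks "Does the Adverse Event Require Study Discontinuation" and routes a yes to the End of Study eCRF. No criterion says when an event requires this.
- **End of Study eCRF (Appendix D).** The choices under "Reason for Discontinuation" include adverse event, investigator judgement, non-compliance, protocol violation and loss to follow-up.
- **Protocol Section 8, removal.** At the physician's discretion "a patient can be removed from the study at any time", without the patient's agreement. The grounds are the patient's interest, non-adherence, a request (patient, sponsor or investigator) and medical judgment.
- **Section 8, continuation.** "Subjects who request discontinuation from the study prior to completion will be encouraged to complete their study follow-up visits, particularly the 6-month visit". The clause that follows allows safety follow-up but does not require it, and it stands in the same sentence about patients who ask to leave. Nothing parallel covers removal by the physician or after an adverse event.
- **Section 8, loss to follow-up.** This needs "failure to complete two consecutive follow-up visits (without due cause) AND documentation of three unsuccessful attempts" to reach the patient or next of kin, including a registered letter.
- **Protocol Section 4.1.** All adverse events are reported until the final follow-up visit, and each is followed until it resolves.
- **Protocol Section 3.1.** The study is observational and "no study activities are experimental".
- **SAP.** The CEA primary endpoint is a percentage of enrolled CEA patients (2.10). Primary patency is a Kaplan-Meier curve (2.11). Survival, reoperation, explant and restenosis get both (2.12 to 2.16). Exits and their reasons are tabulated (2.3). Missing data are handled by listings and descriptive statistics (2.21). No censoring rule is given.

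**The concern.** The patch stays in place whether or not the patient remains in the study, and the study requires no imaging or laboratory tests of its own. Leaving therefore stops no study treatment; it mainly stops the flow of outcome data, in a study whose purpose is to describe safety.

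Exit can follow a complication, and a patient with a complication may plausibly be at higher risk of a later patency loss, reoperation, explant, restenosis, neurologic event or death. If such events go unrecorded, two things can happen:

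- **Kaplan-Meier analyses.** The method assumes that a censored patient has the same later risk as those who stay. If leavers have a higher risk, freedom from the event is overestimated.
- **Crude percentages.** A patient who leaves event-free stays in the denominator and counts as having no event to 6 months. The rate is lowered even when leavers carry only average risk.

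Both effects make the device look better, and nothing in the SAP would show the reader how large they might be.

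**Working it through.** **1. The plan's own figure.** Protocol Section 3.2 gives a target of 100, screen failure of 33%, early termination of 10% and about 166 patients to consent.

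100 / (0.67 × 0.90) = 165.8, rounded up to 166. The stated figure is reproduced.

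It implies 166 × 0.67 = 111 enrolled, of whom 111 × 0.10 = about 11 leave early and about 100 complete. The 10% covers every cause of early termination, so adverse-event and physician removals are only part of the 11.

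**2. Assumptions.** The documents give no event rate, no exit times and no risk for leavers, so ranges are used:

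- 6-month risk p in completers: 5%, 10% or 20%
- exit, free of the endpoint, at month t = 1 or 3
- hazard ratio r after exit, against completers: 1, 2 or 4
- constant hazard h = −ln(1 − p)/6 per month
- fraction leaving d = 11/111 = 0.099, taken to be the same in CEA and non-CEA patients

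**3. Formulas.**

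- Leaver's later risk: q = 1 − exp(−r·h·(6 − t))
- True risk: (1 − d)·p + d·q
- Crude percentage: (1 − d)·p
- Kaplan-Meier risk: 1 − [1 − (1 − d)(1 − exp(−h·t))] × exp(−h·(6 − t))

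**4. One case in full: p = 10%, r = 2, t = 1.**

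- h = 0.1054/6 = 0.01756
- q = 1 − exp(−2 × 0.01756 × 5) = 0.161
- True risk = 0.901 × 0.10 + 0.099 × 0.161 = 0.106
- Crude = 0.901 × 0.10 = 0.090, which is 1.6 points low
- Kaplan-Meier = 1 − (1 − 0.901 × 0.0174) × 0.916 = 0.098, which is 0.8 points low

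**5. All cases, understatement in percentage points.**

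| Hazard ratio after exit | Kaplan-Meier | Crude percentage |
|---|---|---|
| 1 | 0 | 0.3 to 1.7 |
| 2 | 0.2 to 1.4 | 0.5 to 3.1 |
| 4 | 0.7 to 3.5 | 1.0 to 5.2 |

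**6. Worst case: all 11 leavers have an unrecorded event.**

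- 5/111 = 4.5% becomes 16/111 = 14.4%
- 10/111 = 9.0% becomes 21/111 = 18.9%
- 20/111 = 18.0% becomes 31/111 = 27.9%

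The gap is 11/111 = 9.9 points each time.

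**7. Sensitivity to the meaning of 100.** Section 3.2 makes 100 the number completing, whereas Protocol 1.2 and SAP 1.2 call it the enrolment goal. With 100 enrolled and 10 leavers, the results change by about 0.1 point or less.

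**The case against.** The case on the other side has several sound parts.

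- **The triggering event is not lost.** Section 4.1 has it reported and followed to resolution, and the forms ask for an adverse event record when patency is lost, vascular surgery is done or the patch is explanted. The endpoints count patients with at least one event, or time to the first loss of patency. When the triggering event is itself the endpoint, exit costs that endpoint nothing. This stands and limits the loss to later, different endpoint events.
- **Item 13 is a record field.** A reader might infer that it is a stopping rule and should be deleted. Section 8 does not list an adverse event as a ground for removal, so an event leads to exit only through the listed grounds, such as medical judgment. The field and the matching reason also feed the SAP 2.3 disposition table. Deleting them would hide such exits without preventing them.
- **Two missed visits do not end follow-up.** A reader might infer this from Section 8, but the rule also needs the absence of due cause and three failed contact attempts. A patient who cannot be reached has little to collect, so rewriting the rule would gain little.
- **No bias is shown.** A reader might infer that the patients at highest risk are the ones censored and that the results are therefore too favourable. The documents say nothing about who leaves or their later risk, and at hazard ratio 1 the Kaplan-Meier bias is zero.
- **The study is descriptive.** There is no test or threshold, and a 10% rate in 100 patients has a 95% interval of about ±6 points (1.96 × √(0.10 × 0.90/100) = 0.059). The modelled bias is smaller than that.
- **Visits are a burden.** Three office visits may be hard after a disabling event. That argues for record review or contact in place of visits, not for ending outcome collection.

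None of this supplies an instruction to keep collecting outcomes after a removal that the patient did not request, or an analysis that shows how much the missing outcomes could matter.

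**Conclusion.** The point holds as a risk of bias, likely in the device's favour, and not as a demonstrated one. The plan lets participation end after an adverse event or by physician removal, asks only self-requested leavers to continue, and has no analysis for what is then missing. What may be lost is later endpoint events, not the event that led to exit.

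The two types of estimate must be kept apart. Kaplan-Meier results are affected only if leavers carry a higher later risk: up to 1.4 points at hazard ratio 2 and 3.5 at ratio 4. The crude percentages, including the CEA primary endpoint, are low by 0.3 to 1.7 points even at equal risk, and by up to 5.2 at ratio 4. If every leaver had an event, the gap would be 9.9 points.

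Only the 10% early termination comes from the documents. The event risks, exit times, hazard ratios and equal exit fraction across indications are assumptions. Because the 10% covers all causes, the part due to the exits discussed here would be smaller. The change should be made because it is cheap and the lost outcomes cannot be recovered afterwards; it does not invalidate the study.

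**What to change.** **Protocol Section 8.** State that an adverse event, explant, reoperation, non-adherence or physician removal does not end outcome collection. Every implanted patient is followed for endpoints and vital status to 6 months, by record review or contact if office visits stop, unless the patient dies, withdraws consent or cannot be reached.

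**eCRFs.** Keep item 13 and the discontinuation reasons as record fields. The lost-to-follow-up rule can stay as it is.

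**SAP.** State that Kaplan-Meier analyses (2.11 to 2.16 and 2.18) censor patients without the event at last contact. In 2.21, add bounds for early leavers: all event-free, and all with an event. Report these for the CEA percentage as well.

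**Cost.** Wording changes to the protocol and SAP, IRB notification of the amendment, and record review or contact for a few more patients: at most about 11 on the plan's own figures, fewer once deaths, withdrawn consent and true losses are set aside. The consent form was not available for this check, so it should be confirmed that it permits record review after removal.
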